Nothing herein is to be disclosed in any way without the prior express written permission of W. L. Gore & Associates, Inc.

Assessment of the GORE[®] EXCLUDER[®] Conformable AAA Endoprosthesis in the Treatment of Abdominal Aortic Aneurysms

Protocol number: AAA 13-03

07September2022

W. L. Gore & Associates, Inc. Medical Products Division

Study Title	Assessment of the GORE [®] EXCLUDER [®] Conformable AAA Endoprosthesis (CEXC Device) in the Treatment of Abdominal Aortic Aneurysms
Protocol Number	AAA 13-03
IDE or PMA Number	IDE # G150057
Sponsor	W. L. Gore & Associates, Inc.
	[contact]
Study Design	Prospective, nonrandomized, multicenter, study with two parallel substudies:
	Short Neck Substudy : Subjects with abdominal aortic aneurysms having aortic neck angulation $\leq 60^{\circ}$ and infrarenal aortic neck length $\geq 10 \text{ mm}$
	High Neck Angulation Substudy : Subjects with abdominal aortic aneurysms having aortic neck angulation > 60 °and \leq 90° and infrarenal aortic neck length \geq 10 mm
Study Objective	Assess the safety and effectiveness of the CEXC Device for the treatment of infrarenal AAA
Primary Safety Endpoint (Both Substudies)	 Composite of any of the following events through 30 days post-treatment: Death Stroke Myocardial Infarction Bowel Ischemia Paraplegia Respiratory Failure Renal Failure Blood Loss > 1000 mL Thromboembolic Events (including limb occlusion and distal embolic events)

PROTOCOL SUMMARY

GORE CONFIDENTIAL INFORMATION

Primary Safety Endpoint Hypothesis (Both Substudies)	Percentage of subjects free from safety events as adjudicated by the Clinical Events Committee (CEC) at 30 days will be > 79%
Primary Effectiveness Endpoint (Both Substudies)	Treatment success, defined as technical success (defined as successful access and deployment of all required CEXC Device components) and freedom from the following events:
	 Type I endoleak Type III endoleak Migration (10 mm or more) AAA enlargement ≥ 5 mm with or without intervention AAA rupture Conversion to open repair
Primary Effectiveness Endpoint Hypothesis (Both Substudies)	The percentage of subjects with treatment success at one year will be > 80%
Subject Population	Subjects with infrarenal abdominal aortic aneurysm (AAA)
Number of Subjects	Initial Cohort: A total of 175 subjects: 80 Short Neck Substudy, 95 High Neck Angulation Substudy Continued Enrollment Cohort (optional): Up to 15 High Neck Angulation Subjects.
Number of Sites	A maximum of 56 sites located in the U.S.
	The Sponsor shall maintain an updated list of principal investigators, investigational sites, and institutions. This list shall be kept separately from this Protocol.
Expected Time to	Subject accrual – 2 years
Complete Enrollment	Follow-up – 5 years from last subject enrollment
	Total investigation duration – 10 years
	(including site initiation and closing period)
Expected Time of each Study Subject to Complete the Study	Total of 60 months for each subject to complete the study
Pre-Treatment Evaluation	 Physical exam / medical history within 30 days of procedure Serum creatinine concentration Contrast enhanced spiral CT of the abdomen and pelvis ≤ 90 days from procedure
Follow-Up Evaluations	 Follow-up conducted at one, six, and twelve months post- treatment and annually thereafter for five years to consist of: Physical examination Contrast enhanced CT scan
	 Non-contrast CT scan (1 month only)

Significant Inclusion Criteria	 AAA meeting any of the following criteria: Maximum diameter ≥ 50 mm Rapid growth (> 5 mm in a 6 month period) Non-ruptured AAA presenting with clinical symptoms Adequate anatomy to receive the CEXC Device, including: Adequate iliac / femoral access Infrarenal aortic neck diameter 16-32 mm Infrarenal aortic neck length ≥ 10 mm Aortic neck angle ≤ 90° Distal iliac artery seal zone ≥ 10 mm Iliac artery diameter 8-25 mm An Informed Consent Form (ICF) signed by subject Male or infertile female* Able to comply with Protocol requirements including following-up Life expectancy > 2 years Age ≥ 21 years * Infertile female – condition which prevents pregnancy, e.g., hysterectomy, tubal ligation or postmenopausal for greater than 1 year Subjects will be allocated to the appropriate substudy based on the aortic neck angle measurement recorded during screening.
Significant Exclusion Criteria	 Mycotic or ruptured aneurysm Known concomitant thoracic aortic aneurysm which requires surgical intervention Renal insufficiency defined as creatinine > 2.5 mg / dL or patient undergoing dialysis New York Heart Association (NYHA) class IV Aneurysmal, dissected, heavily calcified, or heavily thrombosed landing zone(s) Severely tortuous or stenotic iliac and / or femoral arteries Patient has body habitus or other medical condition which prevents adequate delineation of the aorta Participating in another investigational device or drug study within 1 year of treatment

	 Systemic infection which may increase the risk of endovascular graft infection Known degenerative connective tissue disease, e.g., Marfan or Ehler-Danlos Syndrome Planned concomitant surgical procedure or major surgery within 30 days of treatment date Known history of drug abuse Known sensitivities or allergies to the device materials
Total Expected Duration of the Study	Total investigation duration – 10 years (including site initiation and closing period)
Schedule of Events- All Enrolled Subjects	Screening Pre-Treatment Treatment Discharge Follow-up (30 day, 6 and 12 month and annually through 5 years).
Data Monitoring Committees	Clinical Events Committee (CEC) Data Safety Monitoring Board (DSMB)

1.0 Introduction

This Statistical Analysis Plan (SAP) describes the statistical analyses planned to address the objectives of the AAA 13-03 clinical study. This SAP summarizes the analyses that will be performed to determine the safety and effectiveness of the Gore® EXCLUDER® Conformable AAA endoprosthesis (CEXC Device) when used for the treatment of abdominal aortic aneurysms (AAA). This SAP outlines tables, figures, and listings that are included in reports for the AAA 13-03 clinical study.

1.1 Study Success

In this two parallel substudy design, Gore will define study success on a substudy basis independent from each other.

1.1.1 Short Neck Substudy Success

The Short Neck Substudy is considered successful if both the safety and effectiveness performance goals are met.

1.1.2 High Neck Angulation Substudy Success

The High Neck Angulation Substudy is considered successful if both the safety and effectiveness performance goals are met.

2.0 Study Design Overview

This study is a prospective, multicenter, non-randomized clinical study with two parallel substudies designed to evaluate the safety and effectiveness of the CEXC Device for the treatment of AAA in patients with aortic proximal necks that are short in length and/ or highly angulated in nature. The substudies are described as follows:

Short Neck Substudy: Subjects with AAA having an aortic neck angulation ≤ 60° and an infrarenal aortic neck length ≥ 10 mm

High Neck Angulation Substudy: Subjects with AAA having an aortic neck angulation > 60° and ≤ 90° and an infrarenal aortic neck length ≥ 10 mm

2.1 Enrollment and AE Follow-up

Once the device delivery catheter has been introduced into the Subject's vasculature they are considered an enrolled Subject. Unsuccessful CEXC Device implant Subjects will be tracked for 30 days with all AEs reported. An unsuccessful CEXC Device Subject is defined as a person who underwent an open AAA repair or another stent graft at the time of initial procedure after successful introduction of the CEXC Device delivery catheter, and without CEXC Device system implantation. A patient who either was converted to open AAA repair prior to CEXC Device delivery catheter introduction or whose entire procedure was aborted prior to the CEXC Device delivery catheter introduction is not considered "unsuccessful" as they had not been enrolled in the study. Successful CEXC Device implant Subjects, defined as a Subject with the implantation of the CEXC Device system, will be followed according to the regimen described in **Section 5.2** of the protocol.

2.2 Objectives

2.2.1 Primary Objective(s)

The primary objective of the study is to assess the safety and effectiveness of the CEXC Device for the treatment of infrarenal AAA.

2.3 Design Summary

AAA 13-03 is a non-randomized, multi-center trial that will compare the composite safety and effectiveness endpoints to pre-specified performance goals. A total of 175 subjects will comprise the initial cohort of the study (95 within the High Neck Angulation Substudy and 80 within the Short Neck Substudy)

Subjects will be evaluated through hospital discharge and return for follow-up visits at one (1), six (6), 12, 24, 36, 48 and 60 months.

2.4 Study Endpoints

2.4.1 Primary Safety Endpoint (each substudy)

[figure not shown]
The primary safety endpoint will be a composite of the following within 30 days of the initial procedure based on the definitions provided by Chaikof et al^[1]:

- Death
- Stroke
- Myocardial Infarction
- Bowel Ischemia
- Paraplegia
- Respiratory Failure
- Renal Failure
- Procedural Blood Loss > 1000 mL
- Thromboembolic events (limb occlusion and distal embolic events)

2.4.2 Primary Effectiveness Endpoint (each substudy)

Treatment success: Technical success (defined as successful access and deployment of all required CEXC Device components) and freedom from the following events:

- Type I endoleaks in the 12 month analysis window
- Type III endoleaks in the 12 month analysis window

- Migration ≥ 10 mm between the baseline and the 12 month analysis window
- AAA enlargement ≥ 5 mm with or without intervention between the baseline and the 12 month analysis window
- AAA rupture through the 12 month analysis window
- Conversion to open repair through the 12 month analysis window

The baseline assessment shall occur prior to the end of the one month study window for the Short Neck Substudy and within the first 90 post-operative days for the High Neck Angulation Substudy.

2.4.3 Secondary Endpoints (each substudy)

In addition to the primary effectiveness endpoints for each substudy population, a second group of effectiveness endpoints will be assessed for each substudy at each study follow-up interval (unless indicated otherwise). The endpoints will be reported descriptively and independent of the performance goals. The secondary effectiveness endpoints are defined as the following:

- Aneurysm-related mortality
- Stent fracture based on Core lab analysis (stent fracture will be described as a whole and classified into subclasses that describe their potential impact on CEXC Device proximal fixation.)
- Individual elements of the primary safety and effectiveness endpoints
- Reintervention
- Type II endoleak
- Type IV endoleak
- Index Procedure Blood Loss (initial procedure only)
- Index Procedure Time (initial procedure only)
- Length of Hospital Stay (initial procedure only)

2.5 Statistical Hypotheses

2.5.1 Primary Safety Endpoint (each substudy)

The analysis of the primary safety endpoint is intended to test the hypothesis that the safety of the CEXC Device exceeds the performance goal of 79% freedom from safety composite endpoint in each substudy separately.

The hypotheses are specified as follows:

$$H_0: P_{SE} \le 0.79$$

 $H_A: P_{SE} > 0.79$

2.5.2 Primary Effectiveness Endpoint (each substudy)

The analysis of the primary effectiveness endpoint is intended to test the hypothesis that the effectiveness of the CEXC Device exceeds the performance goal of 80% freedom from effectiveness endpoint events in each substudy separately.

[figure not shown]
The hypotheses are specified as follows:

$$H_0: P_{EE} \le 0.80$$

 $H_A: P_{EE} > 0.80$

Doc Type: GC

2.6 Sample Size Assumptions For the Short Neck Substudy primary safety endpoint, a one sided test with alpha = 0.05, For the High Neck Angulation Substudy primary safety endpoint, one sided test with alpha = 0.05, For the Short Neck Substudy primary effectiveness endpoint, one sided test with alpha = 0.05, For the High Neck Angulation Substudy primary effectiveness endpoint, one sided test with alpha = 0.05, 2.7 Sample Size Calculations 80 Subjects will be utilized in the Short Neck substudy. The High Neck Angulation substudy sample size of 95 Subjects will be utilized.

3.0 Study Treatment Arms

3.1 Test Arm

Patients with AAA are eligible for screening for participation in the study. The study has been designed with standard eligibility criteria to address any known or foreseeable factors that may compromise the outcome of the clinical investigation or the interpretation of results. Only patients who meet all of the Inclusion Criteria and none of the Exclusion Criteria should be enrolled. Gore will not provide any waivers or knowingly allow a patient to be enrolled in the study without meeting all of the described inclusion and exclusion criteria. Subjects will be considered enrolled once the device delivery catheter has been introduced into the Subject's vasculature.

3.2 Control Arm

There is no control arm in this study.

4.0 Study Data Collection

4.1 Study Data Collection Intervals

Subjects will be asked to return for follow-up visits at one (1), six (6), 12, 24, 36, 48, and 60 months post-treatment. At each follow-up visit, subjects will undergo an evaluation for adverse events. Evaluation methods will include a physical examination and spiral CTA of the abdomen and pelvis (non-contrast and contrast spiral CTA required at one (1) month visit) (**Table 1**).

Table 1. Subject Schedule of Events

Diagnostic Test	Pre- treatment	Treatment	1 month	6 months	Annually for 5 years
Physical examination	Х		X	X	X
Creatinine concentration	Х				
Spiral computed tomography (contrast)	х		Х	X	Х
Spiral computed tomography (non contrast)			Х		
Angiography		Х			

4.2 Follow-up Visit Windows

Follow-up visits will be scheduled at appointed times after the date of treatment. The Sponsor recognizes that Subjects may not be able to return for follow-up visits on the exact date required. Thus, a period during which each visit is allowed is demonstrated below (**Table 2**).

Table 2. Follow-up and Associated Visit Windows

Follow-up Visit	ldeal Window	Analysis Window (days)	
Procedure	0	0	
Discharge	Before hospital discharge	n/a	

Post-Procedure	1 - 14	1 - 14
1 Month	23 - 44	15 - 89
6 Months	150 - 210	90 - 242
12 Months	275 - 455	243 - 546
24 Months	640 - 820	547 - 911
36 Months	1005 - 1185	912 - 1275
48 Months	1370 - 1550	1276 - 1640
60 Months	1735 - 1915	1641 - 2006

4.3 Data and Safety Monitoring Board

See **Section 9.6.1** of the protocol for information on the Data and Safety Monitoring Board.

4.4 Clinical Event Committee

See Section 9.6.2 of the protocol for information on the Clinical Events Committee.

5.0 Statistical Analyses

5.1 Analysis Populations

The following populations will be used in various analyses of the data collected in the AAA 13-03 study:

- 1. All Enrolled Subjects This population will consist of all enrolled Subjects
- Safety Eligible Population (each substudy) This population will consist of Initial Cohort Subjects with a follow-up visit at or after 30 days following initial CEXC Device implant procedure. Additionally, any Subjects with an eligible safety event, as defined in Section 2.4.1, even if they did not complete a follow-up visit at or after 30 days following initial procedure, will be included.

3. Primary Effectiveness Population

Short Neck Substudy - This population will consist of Initial Cohort Subjects with both post-op (no later than one month study window) contrast-enhanced CT imaging and a 12 month follow-up visit that included contrast-enhanced CT imaging. Additionally, any Subjects with an eligible effectiveness event, as defined in **Section 2.4.2**, even if they did not complete the necessary follow-up visit or imaging to otherwise be included in the population, will be included.

High Neck Angulation Substudy – This population will consist of Initial Cohort Subjects with both post-op (no later than 90 days) contrast-enhanced CT imaging and a 12 month follow-up visit that included contrast-enhanced CT imaging. If a subject without a 12 month contrast-enhanced CT imaging has post-12 month contrast-enhanced CT imaging at which there was no endpoint event identified by Core Lab (Type I Endoleak, Type III Endoleak, Migration, or Rupture) using the post 12-month contrast CT closest to the 12-month window, the subject will also be included in the analysis. Additionally, any Subjects with an eligible effectiveness

event, as defined in **Section 2.4.2**, even if they did not complete the necessary follow-up visit or imaging to otherwise be included in the population, will be included.

Secondary Effectiveness Populations (each substudy, each endpoint) - These
populations will consist of Initial Cohort Subjects with an evaluable result for the
specific variable.

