5.2 Endpoint Variables

- Death Site reported events.
- Stroke CEC adjudicated site reported events through all follow-up time periods.
- Myocardial Infarction CEC adjudicated site reported events through the 5-year follow-up periods.
- Bowel Ischemia CEC adjudicated site reported events through the 5-year followup periods.
- Paraplegia CEC adjudicated site reported events through the 5-year follow-up periods.
- Respiratory Failure CEC adjudicated site reported events through the 5-year follow-up periods.
- Renal Failure CEC adjudicated site reported events through the 5-year follow-up periods.
- Procedural Blood Loss > 1000 mL Site reported events during initial procedure.
- Thromboembolic events CEC adjudicated site reported events through the 5-year follow-up periods.
- Type I endoleaks Core Lab reported events.
- Type III endoleaks Core Lab reported events.
- Migration Core Lab reported prosthesis or intercomponent migration.
- AAA enlargement Using Core Lab reported data, the measurement closest to 30 days after initial implant will be subtracted from the measurement closest to 365 days after initial implant.
- AAA rupture –Core Lab reported events or CEC adjudicated site reported events through the 5-year follow-up periods.
- Conversion to open repair CEC adjudicated site reported events through the 5vear follow-up periods.
- Aneurysm related mortality CEC adjudicated site reported events through the 5year follow-up periods.
- Stent fracture Core Lab reported events.
- Reintervention CEC adjudicated site reported events through the 5-year follow-up periods.
- Type II endoleak –Core Lab reported events.
- Type IV endoleak –Core Lab reported events.
- Index Procedure Time Site reported during initial procedure.
- Length of Hospital Stay Site reported during initial hospitalization.

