5.4.2 Primary Effectiveness Endpoint Events

Primary effectiveness endpoint events in each substudy will consist of all enrolled Subjects experiencing an event meeting the definition in **Section 2.4.2**.

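### The Primary Effectiveness Population requires that contrast CTs were done, not that the Core Lab could evaluate them, so an unreadable scan by default counts toward success

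*SAP*

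**What the plan says.** **Entry to the primary population (SAP 5.1, item 3).** Both substudies need a baseline scan and a 12 month scan. For Short Neck the baseline is "post-op (no later than one month study window) contrast-enhanced CT imaging"; for High Neck Angulation it may be as late as 90 days. The 12 month condition in both is "a 12 month follow-up visit that included contrast-enhanced CT imaging". Subjects with a known effectiveness event enter regardless of imaging.

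**High Neck Angulation fallback (SAP 5.1, item 3).** A subject who has no 12 month contrast CT may enter on a later contrast CT "at which there was no endpoint event identified by Core Lab".

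**Secondary populations (SAP 5.1).** These are limited to "Initial Cohort Subjects with an evaluable result for the" variable in question. SAP 2.4.3 lists the individual elements of the primary endpoint among the secondary endpoints.

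**Source of events (SAP 5.2).** Type I and Type III endoleaks are events reported by the Core Lab. Migration is "Core Lab reported prosthesis or intercomponent migration". Enlargement is the difference between the Core Lab measurements nearest day 30 and day 365. Rupture may also come from site reports adjudicated by the Clinical Events Committee (CEC), and conversion comes from that source alone.

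**Counting and testing (SAP 5.4, 5.4.2).** Effectiveness events "will consist of all enrolled Subjects experiencing an event meeting the definition in" Section 2.4.2. The test compares a one-sided exact Clopper-Pearson lower bound with the 80% goal, and SAP 5.4 states a Type I error below 0.05.

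**The concern.** Having a scan and having a readable result are different things. The primary population is defined by the first, while three of its six failure events (Type I endoleak, Type III endoleak, migration) can be recorded only through the second. An endoleak that cannot be assessed, a visible leak that cannot be typed, or a graft position that cannot be measured produces no event record, yet the subject stays in the denominator.

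The trial has no control arm (SAP 3.2), so nothing offsets this. An unread subject placed on the success side raises the proportion compared with a fixed goal; none is moved the other way. The same component also carries an evaluability condition in the descriptive secondary table but not in the hypothesis test, where it matters more.

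**Working it through.** **1. What happens to a subject whose 12 month contrast CT the Core Lab cannot read for endoleak or migration**

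- Enters the denominator: yes, because the scan was done (SAP 5.1).
- Type I or III endoleak or migration event: none reported (SAP 5.2), so none counted (SAP 5.4.2).
- Test outcome: a binomial proportion has two categories (SAP 5.4). With technical success and no enlargement, rupture or conversion, the subject falls on the success side by default.
- High Neck fallback: not available, because a 12 month scan exists. A different subject with no 12 month scan and an unreadable later scan does meet the fallback wording, since no event was identified on it.

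**2. The plan's own figure**

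Inputs: goal p0 = 0.80 (SAP 2.5.2); one-sided alpha 0.05 (SAP 2.6); n = 80 and 95 (SAP 2.7). The lower bound for x successes is the 0.05 quantile of Beta(x, n − x + 1). The error is P(Bin(n, 0.80) ≥ r), where r is the smallest passing count.

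- n = 80: r = 71, lower bound 0.8119 (70/80 gives 0.7972 and fails); error 0.0287.
- n = 95: r = 83, lower bound 0.8034 (82/95 gives 0.7913 and fails); error 0.0424.

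Both agree with the stated Type I error below 0.05 when every scan is readable.

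**3. Adding m unread subjects**

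Assumptions: m is fixed and hypothetical, the full n is analysed, readable subjects succeed at exactly 80%, and all m score as successes. The n − m readable subjects then need only r − m successes:

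chance of passing = P(Bin(n − m, 0.80) ≥ r − m).

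Example: n = 95, m = 2 requires 83 − 2 = 81 of 93, and P(Bin(93, 0.80) ≥ 81) = 0.0516. If unread subjects are excluded instead, the threshold is recalculated for n − m.

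| m | n = 80, as success | n = 80, excluded | n = 95, as success | n = 95, excluded |
|---|---|---|---|---|
| 0 | 0.0287 | 0.0287 | 0.0424 | 0.0424 |
| 1 | 0.0322 | 0.0322 | 0.0468 | 0.0468 |
| 2 | 0.0360 | 0.0360 | 0.0516 | 0.0275 |
| 4 | 0.0450 | 0.0450 | 0.0626 | 0.0340 |
| 5 | 0.0501 | 0.0243 | 0.0688 | 0.0378 |
| 10 | 0.0845 | 0.0437 | 0.1081 | 0.0332 |

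Scored as successes, the chance passes 0.05 at m = 5 of 80 (5/80 = 6.25%) and m = 2 of 95 (2/95 = 2.1%). Excluded, it stays below 0.05 at every m tried.

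**4. Effect on a result exactly at the pass threshold, with the m subjects among the successes**

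- n = 80: 71/80 passes (0.8119). Removing 4 gives 67/76 = 0.8025, still a pass; removing 5 gives 66/75 = 0.7999, a fail.
- n = 95: 83/95 passes (0.8034). Removing 1 gives 82/94 = 0.8014, still a pass; removing 2 gives 81/93 = 0.7993, a fail.
- Counted as failures, one such subject reverses either result (70/80 = 0.7972; 82/95 = 0.7913).

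**The case against.** A reader might infer that the SAP scores an unreadable scan as a treatment success. It nowhere says so. SAP 2.4.2 requires freedom from the events, and SAP 5.4.2 defines who has an event without saying that everyone else succeeded, so the score could also be read as undefined. That stands: success is the default result of combining 5.1, 5.2, 5.4 and 5.4.2, not a stated rule.

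The public copy is also incomplete. SAP 5.5.1 to 5.5.4 and 7.1 to 7.2 are not shown, and the protocol is a summary only. A rule for unevaluable reads, or a sensitivity analysis, may exist there. This stands too, but the section defining the population should state or cite such a rule.

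Unread subjects remain exposed to other failures. Enlargement can be scored from another measurable scan, rupture and conversion have site-reported sources, and a second scan within the 12 month analysis window (days 243 to 546, SAP Table 2) could supply an endoleak or migration reading. This narrows the gap to endoleak and migration where no readable scan lies in the window.

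The plan has partial safeguards. The protocol excludes patients whose body habitus or other condition prevents adequate delineation of the aorta, and the secondary tables, with their evaluable denominators, would show how many reads are missing. These limit the problem and make it visible, but they do not change the primary test.

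Finally, the reversals in step 4 start exactly at the threshold, and the Short Neck one is by a hair (0.7999). At 4 unread of 80 the error is still 0.0450. The figures show sensitivity, not an expected effect.

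**Conclusion.** The concern holds as a gap in a stated inclusion rule. The primary population depends on scans being performed, the secondary populations on results being evaluable, and nothing in the text shown says how an unevaluable read is scored in the primary test. By default it counts as freedom from Type I endoleak, Type III endoleak and migration, and relative to exclusion or failure that moves the success rate only upward.

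The size cannot be determined because the documents give no unreadable rate. The 0.05 level is crossed from 5 unread of 80 or 2 of 95 only if readable subjects succeed at exactly 80%, all unread subjects score as successes, and the true rate including them is no better than 80%. High Neck Angulation is more sensitive because its exact error already starts at 0.0424. A reader might also infer that angulated necks give more unreadable scans; the documents contain nothing on this, and the conclusion does not rest on it. Nor do they show that the trial's error rate is in fact inflated.

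**What to change.** In SAP 5.1, item 3:

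- Require an evaluable Core Lab result for Type I endoleak, Type III endoleak and migration in the 12 month analysis window, which any scan in that window may supply. Also require a baseline scan evaluable for migration, and the AAA diameters needed for the enlargement calculation in 5.2.
- Apply the same condition to the High Neck Angulation fallback scan, and let a subject whose 12 month scan is unevaluable use the fallback.
- Keep every subject with a known effectiveness event. Exclude event-free subjects with an unevaluable component from the primary test.
- Add one sensitivity analysis that counts those subjects, and subjects with a leak of undetermined type, as failures.

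If a rule already exists in text not shown, cite it in 5.1 and check it against these points.

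The cost is SAP wording and one table from existing Core Lab data. The denominator shrinks slightly. There is a small conservative bias, because subjects with events always stay in while some event-free subjects leave; the SAP should say so.

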5.4 Statistical Analysis of Endpoints

One-sided exact Clopper-Pearson confidence intervals for binomial proportions (alpha=0.05) will be constructed to test the primary safety and primary effectiveness hypotheses in each substudy. The null hypothesis will be rejected if the lower bounds of the 95% confidence interval estimating device effectiveness and safety exceeds the performance goal. This is equivalent to stating that the estimated effectiveness and safety must exceed the PG with a Type I error rate (alpha) of < 0.05.

All events must meet the protocol definition and will be adjudicated through the CEC process.

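### Aneurysm-related deaths after day 30 but before the 12-month CT, with no listed effectiveness event, leave the effectiveness denominator instead of counting as failures

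*SAP*

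**What the plan says.** - **Safety (SAP 2.4.1).** Death is a component, but only "within 30 days of the initial procedure".
- **Effectiveness (SAP 2.4.2; same components in the Protocol Summary).** Success means technical success plus freedom from Type I or III endoleak, migration, enlargement, rupture and open conversion. No death of any cause is listed. Endoleak counts only if present in the 12-month window, which SAP Table 2 sets at days 243 to 546.
- **Effectiveness population (SAP 5.1, item 3).** Both substudies require an early post-operative contrast CT and "a 12 month follow-up visit that included contrast-enhanced CT imaging". Subjects without the imaging are still included if they had an event listed in 2.4.2. High Neck Angulation also admits a subject whose first contrast CT after the window shows no endpoint event.
- **Aneurysm-related mortality.** SAP 5.2 specifies "Aneurysm related mortality CEC adjudicated site reported events through the" five-year follow-up, so the Clinical Events Committee (CEC) already judges it. SAP 2.4.3 makes it a secondary endpoint, and of that group it says "The endpoints will be reported descriptively and independent of the performance goals".
- **Decision rule (SAP 5.4).** "One-sided exact Clopper-Pearson confidence intervals for binomial proportions (alpha=0.05) will be constructed". "The null hypothesis will be rejected if the lower bounds of the 95% confidence interval estimating device effectiveness and safety exceeds the performance goal". The effectiveness goal is 80% (SAP 2.5.2), and each substudy needs both goals to succeed (SAP 1.1.1, 1.1.2).

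**The concern.** SAP 5.1 already keeps subjects who lack imaging if they had a failure event, so missing scans are not meant to hide failures. Aneurysm-related death is the gravest failure of aneurysm treatment, and that protection does not reach it.

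The path is possible under the plan's own rules. Suppose a subject has a Type I endoleak at the 6-month visit and dies around day 200. The CEC rates the death aneurysm-related, but no rupture, conversion, migration or enlargement is recorded. The endoleak fell before day 243 and is not an event. The death fell after day 30 and is not a safety event. There can be no 12-month CT. The subject is in neither primary event count and not in the effectiveness denominator.

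At stake is the primary effectiveness test. Secondary reporting shows the death but cannot affect a test that is separate from it by design.

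**Working it through.** **Inputs.** One-sided alpha 0.05 and the exact Clopper-Pearson bound (SAP 5.4); goal 0.80 (SAP 2.5.2); N = 80 Short Neck and 95 High Neck Angulation (SAP 2.3). The number of these deaths is not given. It is an assumption here: one death in step 3, and a probability q of 1% to 5% per subject in step 4. Nobody else is assumed missing.

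**Step 1: the plan's own figures.** The sample sizes cannot be re-derived, because the visible text of SAP 2.6 gives no expected rates or power. The decision rule can be rebuilt instead.

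**Step 2: thresholds with nobody excluded.** The lower bound for x successes in n is L = the 0.05 quantile of Beta(x, n − x + 1). The test passes if L > 0.80.
- Short Neck: 71/80 gives L = 0.8119 (pass); 70/80 gives 0.7972 (fail). Exact type I error at a true rate of 80% is 0.029.
- High Neck Angulation: 83/95 gives L = 0.8034 (pass); 82/95 gives 0.7913 (fail). Exact type I error is 0.042.

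Both respect 0.05.

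**Step 3: one death at the threshold.**

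| Substudy | Death dropped | Death counted as failure |
|---|---|---|
| Short Neck | 70/79 = 88.6%, L = 0.8096, pass | 70/80 = 87.5%, L = 0.7972, fail |
| High Neck Angulation | 82/94 = 87.2%, L = 0.8014, pass | 82/95 = 86.3%, L = 0.7913, fail |

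With one death, only these exact counts flip. One success fewer fails even with the death dropped (69/79, L = 0.795; 81/94, L = 0.789). One success more passes under both rules (71/80; 83/95).

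**Step 4: false-pass probability.** Let true success, with these deaths counted as failures, be exactly 0.80. Let each subject have such a death with probability q. Among those who remain, the success rate is 0.80/(1 − q). Then

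P(pass) = Σ over d of Bin(d; N, q) × P[Bin(N − d, 0.80/(1 − q)) ≥ k(N − d)],

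where k(m) is the smallest passing count out of m.

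| q | Expected apparent rate | P(pass), N = 80 | P(pass), N = 95 |
|---|---|---|---|
| 0 | 80.0% | 0.029 | 0.042 |
| 1% | 80.8% | 0.046 | 0.060 |
| 2% | 81.6% | 0.070 | 0.079 |
| 3% | 82.5% | 0.102 | 0.109 |
| 5% | 84.2% | 0.186 | 0.213 |

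As expected numbers of deaths, 1% is 0.8 of 80 or 0.95 of 95, and 3% is 2.4 or 2.85.

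**Step 5: direction.** Against counting the death as a failure, dropping it raises the estimate (87.5% to 88.6% in Short Neck). Against the same subject surviving event-free, it lowers it slightly (71/80 = 88.75% to 70/79 = 88.61%).

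**The case against.** The strongest reply is that few subjects are affected. Fatal rupture needs no CT: SAP 5.2 accepts ruptures reported by a site and adjudicated by the CEC, and SAP 5.1 readmits those subjects without imaging. Conversion works the same way. Deaths to day 30 count against safety. Nothing in the documents shows that even one death of the remaining kind is expected, and the supplied text does not define aneurysm-related mortality. All of this stands, and it limits the likely size.

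The step 3 examples also sit on the threshold. If the true rate among the remaining subjects is assumed to be 90%, the exact count that flips occurs with probability about 13% (70 of 79) and 8% (82 of 94). At 95% it is about 1% and 0.2%. These figures also presuppose that one such death occurs. That stands too.

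Adding a component changes what is compared with the 80% goal, whose derivation is not visible, and it touches the protocol as well as the SAP. This is a fair reason to offer a second option. It is not a reason to leave the deaths uncounted in every comparison with the goal.

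Finally, SAP 5.5 is largely not shown; visible text resumes at 5.5.5. A sensitivity analysis may be there, so its absence cannot be asserted. It would not alter the primary definitions in 2.4.2 and 5.1, which are visible.

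**Conclusion.** The gap is real but narrow: CEC-adjudicated aneurysm-related death, after day 30, before a qualifying 12-month-window CT, in a subject with no event listed in SAP 2.4.2. Such a subject leaves the effectiveness denominator.

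A reader might infer more than the documents support:
- *That every aneurysm-related death after day 30 without rupture or conversion vanishes.* It does not. A subject who dies after an event-free 12-month CT stays in and counts as a success. Technical failure or a qualifying endoleak, migration or enlargement keeps the subject as a failure. A non-fatal safety component by day 30 already counts in the safety endpoint.
- *That a death improves the estimate outright.* It does so only relative to counting the death as a failure.
- *That these are device-related deaths.* The documents speak of aneurysm-related mortality and do not attribute it to the device.

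On size, one death matters only at exactly 70 successes (Short Neck) or 82 (High Neck Angulation). On the assumptions of step 4, the false-pass probability exceeds the stated 0.05 from q = 2% in Short Neck and from q = 1% in High Neck Angulation. The true q is unknown and may be lower. The change is worth making because the effect can be decisive and the variable is already adjudicated.

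**What to change.** In SAP 5.1, keep in the effectiveness population any Initial Cohort subject with a CEC-adjudicated aneurysm-related death before a qualifying 12-month CT, classed as not a treatment success. Put matching wording in SAP 2.4.2 and in the protocol's effectiveness endpoint, so that the two documents stay aligned.

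If the agreed composite cannot change, pre-specify the same calculation as an analysis reported beside the primary test, against the same 80% goal. If the part of SAP 5.5 that is not shown already contains it, a cross-reference is enough.

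The cost is wording in the SAP, and in the protocol for the first option. No new data or visits are needed. The success rate may come out slightly less favourable.
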